4. $\Sigma 5$ nerve conductions include ulnar CMAP, ulnar SNAP, sural SNAP, tibial CMAP, and peroneal CMAP. Their measured values were transformed to normal deviates from percentile values correcting for applicable variables of age, gender, height or weight as based on earlier studies of a large healthy patient reference cohort. Additionally, these percentile values were expressed as points from obtained percentile values (i.e., $> 5^{\text{th}}$ = 0 points; $\leq 5^{\text{th}} - > 1^{\text{st}}$ = 1 point and $\leq 1^{\text{st}}$ = 2 points (and similarly when abnormality is in the upper tail of the normal distribution). The total score is calculated as the mean point scores of the non-missing 5 nerve tests and multiply this value by 5. The maximum total score for $\Sigma 5$ NC is 10.
5. Postural BP test measures autonomic function to address risk of orthostasis. The points are assigned based on change in PBP (> -20 mmHg = 0 points; $> -30 - \leq -20$ mmHg = 1 point; and ≤ -30 mmHg = 2 points).

If at least 1 value at a time point and (replicate) assessment is missing then do the following:

- Missing items within the $\Sigma 5$ NCs component (e.g., missing tibial CMAP) are handled in Step 4 above.

- If 1 of the following components or subcomponents of mNIS+7 (NIS-W, NIS-S, QST-BSA_{TP}, QST-BSA_{HP}, the entire $\sum 5$ NCs, or postural BP) is missing from 1 of the assessments at a time point (“replicate A”), then impute via substituting the component from the other assessment at that time point (“replicate B”) → recover 2 complete replicate mNIS+7 measures A and B at that particular time point.
- If both replicates A and B are incomplete at different components, insert replicate A components into replicate B and replicate B components into replicate A as necessary → allow recovery of 2 complete replicate mNIS+7 measures A and B.
- If NIS-W component is missing from both replicates A & B, mNIS+7 score is considered as missing. If 1 of the other mNIS+7 components or subcomponents (NIS-R, the entire $\sum 5$ NCs, QST-BSA_{TP}, QST-BSA_{HP}, or postural BP) is missing from both replicates A and B, impute this component as the average of the component using data from any of the patients who had non-missing data for that component at the time point.
- If 1 entire mNIS+7 replicate is missing, do not impute the missing replicate; just use the singular (other) replicate rather than the average of the 2 in subsequent calculations.

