3. If the calculated z-score value is greater than upper z-score value (ZUPPER) in the EP table, then the normal deviate value is the minimum of (3.72, (z-score – ZUPPER + WUPPER)).
4. If the calculated z-score value is less than or equal to ZUPPER and greater than the maximum z-score value in the AP table, then the normal deviate value = 2.75.

5. If the calculated z-score falls between 2 values in the AP table, select the z-score with the normal deviate value closer to 0 (i.e., the 50th percentile). The normal deviate value is the value from the Normal Deviate column corresponding to the selected z-score. For example, if PMLAZ = -0.8 then the PMLA normal deviate (PMLAND) value = -1.65. If PMLAZ = 2.2 then PMLAND = 2.37.
6. If the calculated z-score is less than or equal to the z-score corresponding to the 50th percentile and exactly matches a z-score for that parameter in the AP table, then select the row with the next highest z-score value. The normal deviate value is the value from the Normal Deviate column corresponding to the selected z-score. For example, if PMLAZ = -0.9017 then PMLAND = -1.88.
7. If the calculated z-score is greater than the z-score corresponding to the 50th percentile and exactly matches a z-score for that parameter in the AP table, then select the row with the next lowest z-score value. The normal deviate value is the value from the Normal Deviate column corresponding to the selected z-score. For example, if PMLAZ = 2.2682 then PMLAND = 2.37.

The points for the parameters are calculated as follows:

1. For PMLA, TMLA, and VDT: z-scores <1.65 are assigned 0 points, z-scores ≥ 1.65 but <2.33 are assigned 1 point, and z-scores ≥ 2.33 are assigned 2 points.
2. For HRdb, UMAE, PMAK, PMCVK, TMAK, SSAB, and USAW: z-scores > -1.65 are assigned 0 points, z-scores ≤ -1.65 but < -2.33 are assigned 1 point, and z-scores ≤ -2.33 are assigned 2 points.

All Percentiles Table

Percentile	Normal Deviate	HRdb	UMAE	PMAK	PMCVK	PMLA	TMAK	TMLA	USAW	SSAB
0.3	-2.75	-12.783	-5.5287	-4.6320	-9.3076	-1.0017	-7.6549	-0.9448	-4.5129	-2.3235
0.4	-2.65	-12.4944	-5.5287	-4.6320	-9.3076	-1.0017	-7.6549	-0.9448	-4.5129	-2.3235
0.5	-2.58	-12.4944	-5.5287	-4.6320	-9.3076	-1.0017	-7.6549	-0.9448	-4.5129	-2.3235
0.6	-2.51	-12.4944	-5.1192	-4.3753	-8.8001	-1.0017	-7.2749	-0.9037	-4.1808	-2.2050
0.7	-2.46	-12.2499	-5.1192	-4.3753	-8.8001	-1.0017	-7.2749	-0.9037	-4.1808	-2.2050
0.8	-2.41	-12.2499	-4.8488	-4.3712	-8.8001	-1.0017	-7.2270	-0.8394	-3.9289	-2.1063

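### The 1-point band for lower-tail nerve tests has a reversed inequality: mild abnormality gets no score, and severe abnormality qualifies for both 1 and 2 points

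*SAP*

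**What the plan says.** Section 7.1.4 of the SAP closes with two rules that turn nerve test results into 0, 1 or 2 points.

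- **Upper-tail tests** (peroneal and tibial distal latency, VDT): "z-scores <1.65 are assigned 0 points, z-scores ≥ 1.65 but <2.33 are assigned 1 point, and z-scores ≥ 2.33 are assigned 2 points".
- **Lower-tail tests** (HRdb, ulnar, peroneal and tibial CMAP, peroneal conduction velocity, sural and ulnar SNAP): 0 points above -1.65, and then "z-scores ≤ -1.65 but < -2.33 are assigned 1 point, and z-scores ≤ -2.33 are assigned 2 points".

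Section 7.1.1.1, item 4, describes the same points by percentile of the reference population: 0 above the 5th percentile, 1 from the 5th down to but not including the 1st, and 2 at or below the 1st. It lists the tests that enter the mNIS+7 sum: "nerve conductions include ulnar CMAP, ulnar SNAP, sural SNAP, tibial CMAP, and peroneal CMAP". All five fall under the lower-tail rule. The sum is the mean of the available point scores times 5, with a stated maximum of 10.

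**The concern.** In the lower-tail rule the second inequality of the 1-point band points the wrong way. A value that is both ≤ -1.65 and < -2.33 is simply a value < -2.33, so the band sits inside the 2-point band and leaves a gap where mild abnormality should score.

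This line is the operative scoring instruction for a whole component of the mNIS+7, for which Section 4.5 plans summaries of observed values and of change from baseline. Two programmers who follow it literally could produce different scores. How far off they are depends on how the code treats a value that meets no condition, and on which condition wins when two are met.

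**Working it through.** **Inputs.** Cut-offs -1.65 and -2.33 (Section 7.1.4); percentile bands at the 5th and 1st (Section 7.1.1.1, item 4); sum = 5 × mean of non-missing points, maximum 10 (same item); mNIS+7 total 304 (Section 7.1, component table).

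**1. The rule as printed.** {z ≤ -1.65} ∩ {z < -2.33} = {z < -2.33}. Taking each condition literally, against the mirror image of the upper-tail rule:

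| Value | As printed | Mirror of upper-tail rule |
|---|---|---|
| -1.64 | 0 | 0 |
| -1.65 | none | 1 |
| -2.00 | none | 1 |
| -2.32 | none | 1 |
| -2.33 | 2 | 2 |
| -2.34 | 1 and 2 | 2 |
| -3.00 | 1 and 2 | 2 |

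On a grid of 7,441 values from -3.72 to +3.72 in steps of 0.001, 680 values get no score, 1,390 get two scores, and the remaining 5,371 get one.

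**2. The rule with the sign reversed** (1 point if ≤ -1.65 and > -2.33). Every grid value gets exactly one score: 5,370 get 0, 680 get 1 and 1,391 get 2. The result equals the mirrored upper-tail rule at every point. On a standard normal scale the 5th and 1st percentiles are -1.645 and -2.326, so the bands also agree with Section 7.1.1.1. The unscored band holds 0.0495 - 0.0099 = 0.0396, about 4.0%, of a healthy reference population. The SAP does not give the share among patients.

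**3. Effect if unscored nerves are treated as missing and severe nerves keep 2 points.** Let m be the number of mild nerves and s the number of severe ones out of 5, the rest being normal.

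- Correct sum = 2s + m.
- Sum as coded = 5 × 2s/(5 - m).
- Error = m × (2s/(5 - m) - 1).

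| Mild | Severe | Normal | As coded | Correct |
|---|---|---|---|---|
| 1 | 4 | 0 | 10 | 9 |
| 1 | 0 | 4 | 0 | 1 |
| 4 | 1 | 0 | 10 | 6 |
| 4 | 0 | 1 | 0 | 4 |
| 5 | 0 | 0 | missing | 5 |

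The error runs from -4 to +4 points. In the last row, if it occurs in both replicates, the missing-data rule in Section 7.1.1.1 replaces the component with an average over other patients, although all five nerves were measured. Change is distorted too: with four severe nerves, a fifth that worsens from mild to severe shows 10 to 10 instead of 9 to 10.

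**4. Effect if the first condition met decides.** Every value below -2.33 stops at 1 point, so the sum is at most 5 × 1 = 5 against the stated 10. A value of exactly -2.33 would escape the cap. On the normal-deviate scale none of the five tests can take that value, because the lookup steps and their worked examples pass over that row.

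**5. The scale.** The cut-offs are stated for z-scores, but most of the z-score equations in Section 7.1.4 are unscaled residuals. In the All Percentiles Table, the 5th percentile of ulnar CMAP is -3.2846 as a z-score and -1.65 as a normal deviate. An ulnar CMAP z-score of -1.65 lies between the 21st (-1.6695) and 22nd (-1.6377) percentiles. The cut-offs match the 5th and 1st percentiles only when applied to the normal deviate.

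**The case against.** The best reply is that this is an evident typing slip whose correct form is already in the SAP. Section 7.1.1.1 gives complete, non-overlapping percentile bands, the upper-tail rule is printed correctly, and a coding that capped the sum at 5 would clash with the stated maximum of 10. An alert programmer would recover the intent. That is fair, and it is why the correction is not in doubt. It does not make the printed rule usable, and no other section corrects it.

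The size also depends on coding. The cap at 5 needs a first-match chain. If separate statements run in sequence, the 2-point line overwrites the 1-point line, severe nerves score correctly, and only mild nerves are lost. This stands as a condition on the cap.

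The impact is limited. The component is 10 of 304 points. The NIS+7 uses normal deviates and the NIS has no nerve tests, so neither is affected. Section 3.2 rules out formal hypothesis testing, so no error rate or sample size depends on the rule. All of this stands and bears on the weight of the point, not on whether the rule is wrong.

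Finally, naming the normal deviate as the scale is more than a change of one sign. That is correct. Without it, however, the repaired rule would still disagree with the percentile bands in Section 7.1.1.1.

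**Conclusion.** The lower-tail point rule is wrong as written. It leaves the interval above -2.33 up to and including -1.65 unscored and gives every value below -2.33 two scores. It governs all five nerve tests in the mNIS+7.

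The size rests on assumptions about the code. With unscored nerves treated as missing and severe nerves kept at 2 points, the sum is off by 1 point in the simple cases and by up to 4 in either direction, or is wholly missing when all five nerves are mild. With first-match evaluation the sum stops at 5, a loss of up to 5 points. Against the 304-point total, 1 point is 0.3% and 5 points are 1.6%. If the existing program already follows the percentile bands, no result changes and only the text needs correcting; the SAP alone cannot show which is the case.

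**What to change.** In Section 7.1.4, lower-tail point rule, give 1 point to values ≤ -1.65 and > -2.33, and keep the 0-point and 2-point bands as they are. In both point rules, state that the cut-offs apply to the normal deviate, so that they agree with the percentile bands in Section 7.1.1.1.

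Test the scoring program at -1.65, -2.00, -2.33 and -3.00, where it should return 1, 1, 2 and 2. Add -2.05 (1 point), since -2.00 is not an entry in the normal deviate column. Confirm that a measured nerve is never set to missing by the point rule.

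The cost is one inequality sign, a few words on the scale and a programming check. If any interim output was produced with the rule coded literally, the mNIS+7 tables in it would have to be rerun.

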7.2. Norfolk Quality of Life-Diabetic Neuropathy (Norfolk QOL-DN)

Norfolk QOL-DN is a tool for assessing patients' perception of the effects of diabetes and diabetic neuropathy. There are 35 questions divided into 5 domains. The range of possible total scores is -4 to 136.

Part I: Symptoms

Items 1-7 (Part I) are a simple inventory of symptoms of neuropathy. The presence of the symptom is checked in whichever box applies, and an absence of a symptom is checked under "none." Positive responses are scored as 1; and negative responses, as 0.

Part II: Activities of Daily Life

Items 8-35 (Part II) pertain to Activities of Daily Life, and most of these are scaled on a 5-point Likert scale ranging from 0 ("Not a problem") to 4 ("Severe problem"). However, Questions 31 and 32 are scored differently. In Question 31, "Good," the middle item, is scored as 0. "Very Good" is scored as -1, "Excellent" is scored as -2. "Fair" is scored as 1, and "Poor" is scored as 2. In Question 32, "About the Same," the middle item, is scored as 0. "Somewhat better" is scored as -1, "Much better" is scored as -2. "Somewhat worse" is scored as 1 and "Much worse" is scored as 2.

Subscales and Scoring Algorithm

The Total QOL and 5 domains should be summed as follows:

- Total QOL (35 items) $\Sigma(1-7, 8-35)$
- Physical Functioning/Large Fiber (15 items) $\Sigma(8, 11, 13-15, 24, 27-35)$
- Activities of Daily Living (ADLs) (5 items) $\Sigma(12, 22, 23, 25, 26)$
- Symptoms (8 items) $\Sigma(1-7, 9)$
- Small Fiber (4 items) $\Sigma(10, 16, 17, 18)$
- Autonomic (3 items) $\Sigma(19, 20, 21)$

The total score and domain scores are calculated without weighting of any kind, and reported as the integer sum of the listed questionnaire items.

If at least 50% of the items are non-missing, domain scores are calculated as the average scores of non-missing included items multiplied by the number of items in the domain, rounded to the nearest integer. A domain score is missing if more than 50% of the included items are missing.

If the scores for all 5 domains are non-missing, then Total QOL is the sum of scores of the 5 domains; however, if at least 1 of the domains is missing and at least 50% of the items (18 items) are non-missing, then Total QOL is calculated as 35 times the mean of the non-missing items, rounded to the nearest integer. Otherwise, Total QOL is deemed as missing.

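### SAP Section 7.2: prorating Norfolk QOL-DN averages 0-to-4 items with Questions 31 and 32 (-2 to +2), so Physical Functioning and the 35-item fallback can be shifted or leave the possible range

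*SAP*

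**What the plan says.** All of the scoring is in SAP Section 7.2.

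- **Part I, items 1 to 7:** "Positive responses are scored as 1; and negative responses, as 0". The number of boxes per item is not stated.
- **Part II, items 8 to 35:** "most of these are scaled on a 5-point Likert scale ranging from 0" to 4. "However, Questions 31 and 32 are scored differently": each runs from -2 to +2 with the middle answer at 0. Question 31 is an overall rating from Excellent to Poor. Question 32 is a change question from Much better to Much worse.
- **Range:** "The range of possible total scores is -4 to 136".
- **Weighting:** "The total score and domain scores are calculated without weighting of any kind".
- **Missing items in a domain:** when at least half are answered, "domain scores are calculated as the average scores of non-missing included items multiplied by the number of items in the domain", rounded to an integer.
- **Missing domain:** if at least 18 items are answered, "then Total QOL is calculated as 35 times the mean of the non-missing items, rounded to the nearest integer".

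Questions 31 and 32 both belong to the 15-item Physical Functioning/Large Fiber domain. Section 7.2 has no special rule for them when items are missing, and it does not truncate to the stated range. Section 3.10.1 sends the result of partial imputation into all analyses.

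**The concern.** Multiplying a mean by the number of items replaces each missing item with the mean of the answered ones. That is reasonable when the items share a scale. Here two of the fifteen do not, because they are centred 2 points lower.

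If Questions 31 and 32 are skipped, they receive a value typical of the 0-to-4 items. If 0-to-4 items are skipped, Questions 31 and 32 pull the filled-in values down. The direction of the error therefore depends on which items were left blank.

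Section 4.5 summarises the total and every domain score, with change from baseline for the total. A patient with a complete form at one visit and a prorated one at another can show a change that comes from the scoring. Section 3.2 reports minimum and maximum, so an impossible score would be visible in a table.

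**Working it through.** **Stated range.** Minimum: 2 × (-2) = -4. Maximum: 26 Part II items × 4 = 104, plus 2 × 2 = 4 for Questions 31 and 32, plus Part I. With up to 4 points per Part I item, 104 + 4 + 28 = 136, which reproduces the SAP. With at most 1 point per Part I item the maximum is 104 + 4 + 7 = 115, which does not. I therefore take items 1 to 7 as scoring up to 4. This is inferred from 136, not stated.

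**Which scores are affected.** On that reading the Activities of Daily Living, Symptoms, Small Fiber and Autonomic domains hold only 0-to-4 items. Only Physical Functioning and the 35-item fallback mix scales. Physical Functioning runs from -4 to 13 × 4 + 2 × 2 = 56, whatever Part I scores.

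**Extremes under the rule.** At least 8 of 15 domain items must be answered.
- Domain, high: Questions 31 and 32 missing, the other thirteen at 4: 15 × 4 = 60, above 56. With the other domains at maximum the total is 136 - 56 + 60 = 140.
- Domain, low: seven 0-to-4 items missing, six at 0, Questions 31 and 32 at -2: 15 × (-4/8) = -7.5, below -4.
- Fallback, high: 35 × 4 = 140. Fallback, low: 35 × (-4/18) = -7.8, rounded to -8.

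**Shift away from the extremes.** Assume the same relative level on every item: x on the 0-to-4 items and x - 2 on Questions 31 and 32. The full domain score is 13x + 2(x - 2) = 15x - 4. With n items answered, k of them from Questions 31 and 32, the prorated score is 15(nx - 2k)/n = 15x - 30k/n. The error is 4 - 30k/n, whatever x is.

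| Missing | n | k | Error in points |
|---|---|---|---|
| Questions 31 and 32 | 13 | 0 | +4.0 |
| One of them | 14 | 1 | 4 - 30/14 = +1.86 |
| One 0-to-4 item | 14 | 2 | 4 - 60/14 = -0.29 |
| Five 0-to-4 items | 10 | 2 | 4 - 60/10 = -2.0 |
| Seven 0-to-4 items | 8 | 2 | 4 - 60/8 = -3.5 |

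Example: at x = 2 the full score is 26. With Questions 31 and 32 missing the rule gives 30, which amounts to filling in Poor and Much worse where the mid-scale answers are Good and About the Same.

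**A different assumption.** Suppose both questions are missing, their true answers are the middle ones (0), and the other thirteen average m. The full score is 13m and the rule gives 15m, an error of 2m: +1 at m = 0.5 and none at m = 0.

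**The rescaled rule.** Adding 2 to Questions 31 and 32, averaging, multiplying and subtracting 4 gives 15 × 0 - 4 = -4 to 15 × 4 - 4 = 56 for the domain, and -4 to 35 × 4 - 4 = 136 for the fallback. A complete form is unchanged, because the two added 2s equal the 4 subtracted. The example above returns 26.

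**The case against.** The arithmetic is not in dispute, but several limits are fair.

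- **Extreme cases.** With Questions 31 and 32 missing, exceeding 56 before rounding needs a mean above 56/15 = 3.73 on the other thirteen items. The -7.5 needs every answered 0-to-4 item at 0, the best answer to both questions, and seven blanks. This stands.
- **Size rests on an assumption.** Question 32 asks about change, so it need not follow current severity. If the true answers are the middle ones, the error is small for patients with few problems. This stands too.
- **The rescaling is not better everywhere.** A patient with 0 on all thirteen items and both questions blank gets 0 for each under the SAP, but -2 for each (Excellent, Much better) after rescaling. If the true answers are the middle ones, the rescaled error is 2(m - 2) against 2m, so the SAP rule is closer when m is below 1. This must be disclosed with the fix.
- **Low consequence.** Section 3.2 plans no hypothesis tests, and Norfolk is one of many measures. A single skipped 0-to-4 item moves the score by about 0.3 points, mostly lost in rounding.

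A reader might infer that every Norfolk domain is faulty. On the reading that the stated 136 requires, four of the five are not. If Part I items carried at most 1 point, Symptoms would share the fault: items 1 to 4 missing, 5 to 7 at 1 and item 9 at 4 gives 8 × 7/4 = 14 against a maximum of 11. The stated range does not support that reading.

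**Conclusion.** The point holds within limits. In Physical Functioning and in the 35-item fallback, Section 7.2 averages items on different scales, and at the floor or ceiling the result can contradict the range that the same section states. Those out-of-range values follow from the scoring rules alone. The shifts of +4, +1.9, -0.3 and -3.5 points also need equal relative severity across items. They compare with a total range of 140 points (-4 to 136).

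A reader might go further and infer that the reported group means or changes are biased in a known direction. The SAP does not support that: the sign depends on which items are blank, and no item-missing rate is given. The effect on group means is probably small and cannot be derived.

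Priority is minor. The study is descriptive, and Section 4.5 does not require Study 003 patients to complete the questionnaire.

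**What to change.** Add to Section 7.2: when a Physical Functioning score or the 35-item fallback total is prorated, add 2 to Questions 31 and 32 before averaging, multiply the mean by the number of items (15 or 35), then subtract 4. The fallback part relies on items 1 to 7 scoring up to 4, so the section should state how many points each Part I item can carry.

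Apply the rule at follow-up and at baseline, including baseline values carried from the parent study under Section 3.4. Report how many scores were prorated at each visit.

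The cost is a sentence or two in the SAP and about one line of code, plus rescoring of any prorated parent-study baselines. There are two downsides. A few scores may differ from those reported in the parent study. For patients with very low item scores, missing Questions 31 and 32 are filled in near -2. A sensitivity summary that sets them to 0 would show whether this matters.

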7.3. EuroQOL-5-Dimension 5-Level (EQ-5D-5L)

Each of the 5 dimensions (Mobility, Self-Care, Usual Activities, Pain/Discomfort, Anxiety/Depression) is scored on a 5-point Likert scale from 1 ("I have no problems/pain/anxiety") to 5 ("I am unable to...", "I have extreme anxiety/depression").

The 5 scores are concatenated together (in the order of Mobility, Self-Care, Usual Activities, Pain/Discomfort, Anxiety/Depression) to create an EQ-5D-5L profile (e.g., 11111, 55555). The

profile is then used to obtain an index value using the United States value set. The index values range from -0.109, associated with a profile of 55555, to 1.0, associated with a profile of 11111. Smaller index values indicate greater impairment.

Missing values are handled as follows:

- Missing items are coded as “9” in creating patient profiles.
- The index value is deemed as missing when responses are missing for 1 or more of the 5 dimensions.
- If the entire instrument is missing, the EQ-5D-5L index value is considered as missing.

